### **9.6. Safety Oversight**

The ISM is a physician at the enrollment site with relevant expertise whose primary responsibility is to provide independent safety monitoring in a timely fashion at each site. The primary focus of the ISM is to independently review all SAEs, thoroughly investigate those events considered unexpected, and provide an independent assessment to the FDA. Participation is for the duration of the study. The ISM will review available safety data provided for each subject after each study arm prior to making a recommendation to proceed to the next study arm. A “study arm” encompasses the administration of the product (patches or IV) and all associated procedure days. Ad hoc meetings with the FDA and MAI/PI may be required if a halting rule occurs. The ISM should be able to readily access all subject records in real time. This is accomplished by review of SAEs, immediately after they occur, with follow-up through resolution, or until the MAI/ISM deems the subject medically stable.

The ISM may be a faculty member at the clinical site, but will not be under the direct supervision of the PI. It is the responsibility of the PI to ensure that the ISM is apprised of all new safety information relevant to the study product and the study. This includes providing the ISM with all safety reports issued by the sponsor. The ISM should receive all protocol revisions and may receive other documents related to the study. The ISM will review all SAEs which occur during the course of the study. The ISM may transiently halt enrollment. The ISM will contact the MAI and PI, and the medical officer at the FDA for any event that needs further evaluation.

## 9.7. Clinical Monitoring

### 9.7.1. Site Monitoring Plan

Site monitoring is conducted to ensure that the human subject protection, study procedures, laboratory, study product administration and data collection processes are of high quality and meet sponsor, ICH E6, and other appropriate, regulatory guidelines and that the study is conducted in accordance with the protocol and sponsor standard operating procedures. Site visits may be conducted by an authorized representative of the FDA or other regulatory agencies to inspect study data, subjects' medical records and CRFs in accordance with ICH guidelines, Good Clinical Practice (GCP) and the respective local and national government regulations and guidelines. The investigator will permit authorized representatives of the FDA and the respective local and national health or regulatory authorities to inspect facilities and records relevant to this study if needed. The PI and MAI will provide direct access to all study-related sites, source data/documents, and reports for the purpose of monitoring and auditing by the Sponsor, and inspection by local and regulatory authorities.

FDA-designated clinical monitors will verify that the clinical study is conducted and data are generated, documented (recorded), and reported in compliance with the protocol, GCP, and the applicable regulatory requirements. Clinical monitoring reports will be submitted to the FDA.

## 10. PHARMACOKINETICS AND STATISTICAL CONSIDERATIONS

### 10.1. Study Hypotheses

The main objective of this study is to determine the absolute bioavailability and PK parameters (e.g., AUC,  $C_{max}$ ,  $T_{max}$ , CL, V) of lidocaine in healthy adults after using lidocaine 5% patches manufactured by Endo Pharmaceuticals and Mylan. The secondary objective is to determine residual drug content in worn patches.

### 10.2. Pharmacokinetic (PK) Analyses

Lidocaine concentrations will be measured in serum samples collected from each subject. Blood samples (approximately 5 mL each) will be collected at the time points list in **section 4**. Actual sampling times will be used to estimate PK parameters.

Non compartmental and compartmental analyses will be conducted to estimate the primary PK parameters such as clearance (CL), volume of distribution (V), elimination rate constant ( $K_{el}$ ), maximum serum concentration ( $C_{max}$ ), time of maximum serum concentration ( $T_{max}$ ) and area under the serum concentration-time curve (AUC). Absolute bioavailability will be calculated as follows:

$$\text{Absolute bioavailability} = \frac{AUC_{patch}/Dose_{patch}}{AUC_{IV}/Dose_{IV}}$$

**Equation 1:** For determination of the absolute bioavailability for the Lidoderm® 5% patches (Endo Pharmaceuticals) and the lidocaine 5% patches (Mylan). The patch refers to the topical lidocaine patch systems. The geometric means for  $AUC_{0-\infty}$  will be obtained by exponentiating the log transformed  $AUC_{0-\infty}$  for the two treatments to determine the absolute bioavailability.

Different mathematical approaches including, but not limited to, deconvolution will then be utilized to determine secondary objectives and the rate of drug delivery from the patches. The secondary objective to determine residual drug content in worn patches would provide a surrogate method to determine the amount of drug delivered *in vivo* after wearing the patch. The following equation will be used to determine the amount of drug delivered *in vivo*:

$$\text{Lidocaine released} = \text{Total lidocaine} - \text{residual lidocaine}$$

**Equation 2:** The cumulative amount of lidocaine released by Lidoderm® 5% patches (Endo Pharmaceuticals) or lidocaine 5% patches (Mylan) at the end of the study arm will be obtained by subtracting residual lidocaine still remaining in the patch at the end of the study arm from the total amount of the drug present in an unused patch.

Further calculation will determine the rate of drug release from the patches using the following equation:

$$\text{Release rate} = \frac{\text{Lidocaine released}}{\text{Application duration}}$$

**Equation 3:** Determination of lidocaine release rate using the amount of lidocaine released from the patches.

Finally, the lidocaine absorption rate will be calculated using steady state concentrations ( $C_{ss}$ ) and the clearance (CL) as predicted from the IV bolus data:

$$Absorption\ rate = C_{ss} \times CL$$

**Equation 4:** Determination of the absorption rate from lidocaine patches using the steady state concentrations and the clearance.

A detailed explanation of the statistics to be performed on the PK analysis is presented in **Section 10.4.**

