The study has been designed to reduce these potential side effects as follows. The dosing regimen in this study is 0.5 mg/kg IV lidocaine administered as a slow push over 5 minutes. This dose was selected based on previous studies in human subject in which IV lidocaine has been administered to humans in ranges from 0.5 mg/kg to 2.2 mg/kg. We selected a low dose to reduce the risk of side effects but still allow detection of drug serum concentrations for calculating PK parameters. In a heart with normal conduction and normal sinus rhythm, therapeutic levels of lidocaine cause little or no decrease in A-V conduction, and minimal cardiac slowing. Lidocaine also has minimal hemodynamic effects in normal subjects, and causes minimal to no decrease in ventricular contractility, cardiac output, arterial pressure, or heart rate. Rapid IV bolus injections would lead to very high blood levels very quickly, which would be more likely to cause depressed cardiac function than a slowly administered IV injection given over 1 – 5 min. For this reason, the IV injection in this study will be administered slowly over 5 minutes. Subjects will be connected to a SureSigns VM4 portable bedside monitor during the injection and for one hour after, for continuous noninvasive monitoring. This monitor has a 3-lead electrocardiogram (ECG) to monitor heart rate and rhythm, a pulse oximeter to monitor oxygen saturation (SpO2) and non-invasive blood pressure monitoring (NBP) capability. This is similar to monitoring that has been described previously in human subjects receiving IV lidocaine and is also in agreement with the University of Iowa Hospitals and Clinics (UIHC) nursing committee protocol for monitoring with lidocaine injections. These parameters will be measured again prior to the subject leaving at the end of the procedure day. The Medically Accountable Investigator (MAI) (i.e., licensed clinician) will be in the hospital during all IV studies and will be available for consultation in the event that serious adverse events occur.

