### 5.1. Subject Inclusion Criteria

Subjects are eligible for this study if they fulfill the inclusion criteria specified below:

1. Men or non-pregnant women, of any ethnic background, between the age of 18 and 65 years old.
2. Provide written informed consent before initiation of any study procedures.
3. Available for follow-up for the planned duration of the study.
4. Able to communicate well with the investigators.
5. Demonstrate comprehension of the protocol procedures and knowledge of study, as demonstrated by a study member filling out a consent checklist form to verify that the subject understands all aspects of the study including the purpose, procedures, risks and benefits.
6. Able to adhere to the study protocol schedule, study restrictions and examination schedule.
7. Subjects must be non-smokers and not regular users of tobacco. They must have refrained from regular and habitual use of nicotine-containing substances, including tobacco products (e.g., cigarettes, cigars, chewing tobacco, gum, patch or electronic cigarettes) over the previous 12 months and must have not used any nicotine-containing products in the previous 30 days.
8. Subjects who are within their ideal body weight (BMI between 18-29.9 kg/m^2).
9. Subjects deemed to be healthy as judged by the Medically Accountable Investigator (MAI), as determined by medical history, physical examination, and medication history.
10. Negative urine drug screening test.
11. Have a normal blood pressure (systolic: 90-139 mmHg; diastolic: 60-89 mmHg) and heart rate (55-100 bpm).
12. Have normal screening laboratories for WBC, Hgb, Hct, platelets, sodium, potassium, chloride, bicarbonate, BUN, creatinine, ALT, AST.
13. Female subjects must be of non-childbearing potential. This is defined as surgically sterile (i.e. history of hysterectomy or tubal ligation), or postmenopausal for more than 1 year (no bleeding for 12 consecutive months). If the person is of childbearing potential they must be non-pregnant at the time of enrollment and on the morning of the first day of each study treatment procedure day (a urine pregnancy test will be administered if it has been >30 days since serum pregnancy test for enrollment). The person must also agree to use hormonal or barrier birth control such as implants, injectables, combined oral contraceptives, some intrauterine devices (IUDs), sexual abstinence, or a vasectomized partner.

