After signing of the informed consent document a screening visit will be scheduled. It is possible for the screening visit to take place on the same day as the informed consent visit if scheduling allows. Screening evaluations will include:

- Questions about demographic information, medical history, and medication history
- Vital signs to determine blood pressure, pulse, temperature, and respiratory rate
- Height and weight
- ECG
- A brief physical exam, performed by the MAI or his designee
- Primary Skin Irritation (PSI) assessment for the site of patch application, completed by a study team member
- Urine drug of abuse screen
- Approximately 40 mL of blood will be collected from an arm or hand vein to test for the following:
  - Hematology parameters including Hgb, Hct, WBC and platelets
  - Chemistry parameters including sodium, potassium, chloride, bicarbonate, BUN, creatinine, AST, ALT
  - Serum pregnancy test (if female of childbearing potential)

Subjects will satisfy all inclusion/exclusion requirements. All screening results will be evaluated against the inclusion/exclusion criteria to confirm subject eligibility (as defined in **section 5.1 and 5.2**). Laboratory results must be within the acceptable ranges in **Appendix B**; abnormal values may be repeated if believed to be a transient and non-clinically significant value. Any clinically significant abnormal laboratory will be shared with the subject and the subject will be advised to follow-up with their physician.

Subjects will be compensated for their time which is calculated as follows:

Screening visit:	\$50
Procedure Day 1:	\$175
Procedure Day 2:	\$75
Procedure Day 3:	\$25
Procedure Day 4:	\$175
Procedure Day 5:	\$175
Procedure Day 6:	\$100
Procedure Day 7:	\$25
Bonus completion of all visits:	\$100
Total compensation:	\$900.00

The money will be mailed directly from Accounts Payable to the subject in the form of a check for a total of \$900.00. This payment schedule is based on the volunteer completing all study procedures. Failure to meet study requirements will result in a prorated payment determined by subject completion. This payment schedule will be followed for subjects in both groups.

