#### **7.3.4. Procedure Day 4: Lidocaine HCl Injection, 20 mg/1 ml Preservative Free Single Dose Vials**

- Subject will return to the CRU after a minimum washout period of 48 hours from the last blood draw from Arm 1 of the study.
- Study staff will review any changes in medical history, medication history, and other study qualifications. All inclusion/exclusion criteria must continue to be met.
- Vital signs to determine blood pressure, pulse, temperature, and respiratory rate will be performed within the 60 minutes prior to injection of lidocaine HCl.
- Urine pregnancy test will be obtained from women of childbearing potential if it has been more than 30 days since their last pregnancy test; the test must be negative.
- The IV catheter will be placed under aseptic technique by an experienced nurse in the CRU.
  - Approximately 5 mL of blood will be drawn within the 60 minutes prior to the injection of lidocaine HCl.
- The SureSigns VM4 monitor will be setup and attached to the subject for continuous monitoring of ECG, SpO2, and blood pressure. Monitoring will start 5 minutes before administration of the IV lidocaine and will continue during and for one hour after the injection.
- Time 0: Using aseptic technique, an experienced nurse in the CRU will place an intravenous catheter in the opposite arm from the IV catheter used for blood sampling; this second catheter will be used for the IV lidocaine injection. Lidocaine HCl injection, 20 mg/1 ml preservative free single dose vials, dose 0.5 mg/kg, will be intravenously administered over 5 minutes using an Alaris Guardrails pump with syringe pump cassette. The catheter will be removed immediately upon completion of the injection.
- Blood sample collection will begin after the full injection has been administered. Approximately 5 mL of blood will be drawn by an experienced nurse in the CRU at the following time points after injection of the lidocaine HCl:
  - 2 minutes after the lidocaine HCl injection
  - 5 minutes after the lidocaine HCl injection
  - 10 minutes after the lidocaine HCl injection
  - 20 minutes after the lidocaine HCl injection
  - 30  $\pm$  5 minutes after the lidocaine HCl injection
  - 45  $\pm$  5 minutes after the lidocaine HCl injection
  - 1:00 hour  $\pm$  5 minutes after the lidocaine HCl injection (SureSigns VM4 monitor removed)
  - 2:00 hours  $\pm$  5 minutes after the lidocaine HCl injection (vital signs obtained)

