### 10.4. Statistical Analysis Plan

Primary statistical analysis will be performed on the natural log transformed  $AUC_{0-t}$ ,  $AUC_{0-\infty}$  and  $C_{max}$  of lidocaine from the two treatments. The following will be obtained:

- A linear mixed effects model will be used to assess the effects of treatment, period, sequence, and subject within sequence on the natural log transformed  $AUC_{0-t}$ ,  $AUC_{0-\infty}$  and  $C_{max}$  of lidocaine. For this, the treatment, period, and sequence effect will be treated as fixed effects (assessed at a significance level of 0.05) while the subject within sequence will be treated as a random effect.
- Intra- and inter-individual variabilities will be obtained.
- The least squares mean estimates for the adjusted differences between treatment means (the log transformed  $AUC_{0-t}$ ,  $AUC_{0-\infty}$  and  $C_{max}$ ) and the standard error associated with these differences will be obtained.
- The 95% confidence intervals for absolute bioavailability of the lidocaine patches will be obtained.

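### Equation 1 takes absolute bioavailability from geometric means of AUC with an undefined IV dose, although the IV dose varies with body weight; read literally, this gives a 95% interval that is too wide

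*Combined protocol and SAP*

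**What the plan says.** - **IV dose.** Section 2.3.1 states: "The dosing regimen in this study is 0.5 mg/kg IV lidocaine administered as a slow push over 5 minutes". The procedures repeat this for both groups (sections 7.3.4 and 7.3.11): "dose 0.5 mg/kg, will be intravenously administered over 5 minutes". The mg dose is therefore proportional to body weight.
- **Body size.** The only limit in section 5.1 is "BMI between 18-29.9" kg/m². No weight or height range and no weight distribution is given. Both sexes are eligible. "Height and weight" are recorded at screening (section 7.1).
- **Patch dose.** Every subject wears three patches of each product, at 700 mg (Lidoderm, section 6.3.1) or 140 mg (Mylan, section 6.3.3) per patch.
- **Equation 1 (section 10.2).** F is AUC_patch/Dose_patch divided by AUC_IV/Dose_IV, with no subject index and no definition of Dose_IV. The legend says that the geometric means of AUC0-∞ are used "for the two treatments to determine the absolute bioavailability". It does not mention dividing AUC_IV by dose before averaging.
- **Section 10.4.** "Primary statistical analysis will be performed on the natural log transformed" AUC0-t, AUC0-∞ and Cmax, without dose normalisation. Its last item reads: "The 95% confidence intervals for absolute bioavailability of the lidocaine patches will be obtained". No construction is given, although section 10.2 refers to 10.4 for the statistical detail.

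**The concern.** The legend averages AUC within each treatment. It does not average AUC/Dose, and it does not average F over subjects. With a fixed patch dose and a weight-based IV dose, no single mg value belongs in the denominator, so the analyst has to choose one.

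The choice matters because the design is paired. Clearance cancels within a subject, which is the purpose of the IV arm. Contrasting raw log AUCs cancels clearance but leaves in the subject's log IV dose, which is log weight plus a constant. Weight variation then counts as noise in the interval for the main objective. Two analysts could also report different estimates and intervals from the same data.

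**Working it through.** **The plan's own figure.** No value or precision for F is stated, so there is none to reproduce. The one related figure is the 24 subjects in section 10.3. Two one-sided tests at 5% each, with 22% within-subject CV, a 5% difference and limits of 0.80 to 1.25 (the limits are assumed; the plan does not state them), give 22 subjects for 80% power. Power at 24 is 83.8% to 84.7%. That calculation compares patch with patch and does not involve Equation 1.

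**Algebra.** For subject i, with the same clearance in both periods (the premise of Equation 1):

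ln AUC_patch,i − ln AUC_IV,i = ln F_i + ln Dose_patch − ln Dose_IV,i

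Dose_patch is constant and Dose_IV,i = 0.5 × weight_i. Hence:

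- own dose used: SD of the paired quantity = SD(ln F)
- raw AUC with one Dose_IV: SD = √[SD(ln F)² + SD(ln weight)²], if F is independent of weight

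**Interval width.** The half-width on the log scale is t × SD/√24, with t = 2.069 on 23 degrees of freedom. Two assumed values of SD(ln F) are used:

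- 0.307 = √[2 × ln(1 + 0.22²)], which puts the plan's 22% CV on each AUC and allows no further spread in F between subjects
- 0.555 ≈ √[ln(1 + 0.60²)], a 60% CV for F

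| SD(ln F) | SD(ln weight) | Own dose | Raw AUC | Excess width |
|---|---|---|---|---|
| 0.307 | 0.10 | 0.130 | 0.137 | 5% |
| 0.307 | 0.15 | 0.130 | 0.145 | 11% |
| 0.307 | 0.19 | 0.130 | 0.153 | 18% |
| 0.307 | 0.22 | 0.130 | 0.160 | 23% |
| 0.555 | 0.10 | 0.234 | 0.238 | 2% |
| 0.555 | 0.22 | 0.234 | 0.252 | 8% |

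Example, fourth row: √(0.307² + 0.22²) = 0.378, and 0.378/0.307 = 1.23.

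**Coverage.** A simulation with SD(ln weight) 0.19 and 22% CV per AUC gave a raw-AUC interval 17.6% wider. Its coverage was 97.6% with the geometric mean dose and 97.1% with the arithmetic mean dose, against 95.1% when each subject's own dose was used.

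**Point estimate.** The mean of ln Dose_IV,i is the log of the geometric mean dose. Using the geometric mean dose as Dose_IV therefore gives exactly the geometric mean of F_i. Using the arithmetic mean multiplies F by the ratio of arithmetic to geometric mean dose, √(1 + CV²) for log-normal weight: 1.005 at CV 10%, 1.011 at 15%, 1.020 at 20% and 1.031 at 25%.

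**The two weight ranges differ slightly.** A CV of 25% is SD(ln weight) = √[ln(1 + 0.25²)] = 0.246, just beyond the 0.22 in the table. At 0.246 with SD(ln F) 0.307 the excess would be √(1 + 0.246²/0.307²) − 1 = 28%.

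**The case against.** The strongest reply is that Equation 1 contains the dose division, so it is dose-normalised in form and can be applied subject by subject. Subjects are their own controls, and the clearance that section 10.2 estimates from the IV data already needs each subject's mg dose. Read that way, no weight variation is carried over. The equation does allow this reading. The legend, however, names AUC0-∞ by treatment as the quantity averaged, and nothing in the plan states the per-subject step. A reader therefore cannot claim that the plan has committed to the wrong calculation, only that its literal wording leads there.

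A reader might infer three stronger things, and the documents support none of them:

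- **That the mg dose differs more than two-fold between subjects.** The BMI limits alone allow 29.9/18 = 1.66-fold at equal height. Passing two-fold needs opposite BMI extremes and a height ratio above √(2/1.661) = 1.097. The criteria permit this but do not imply it. Among 24 subjects its probability runs from about 0% to 95% as the assumed weight CV goes from 10% to 25%.
- **That F is necessarily biased upward.** This needs an arithmetic mean dose, which the plan never specifies. A geometric mean dose, which would match the averaging in the legend, gives no bias.
- **That the mixed model in section 10.4 is at fault for using raw log AUC.** The IV arm is the middle period in both groups, so that model could not separate an IV effect from a period effect. The model is most coherently read as patch versus patch, where dose is the same for every subject and no weight term arises.

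It is also fair to say that the excess width is conservative under the stated assumptions, that no decision rule depends on it, and that pairing still removes each subject's clearance.

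**Conclusion.** The point holds as a matter of method and precision. The legend gives an averaging rule that, followed literally, yields a less precise interval for the main objective than the same data allow, and Dose_IV is left undefined. The 95% interval for F is about 2% to 23% too wide for SD(ln weight) 0.10 to 0.22 and SD(ln F) 0.31 to 0.56. The estimate of F is unchanged with a geometric mean dose and about 0.5% to 3% too high with an arithmetic mean dose (weight CV 10% to 25%).

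None of these spreads is in the documents. Independence of F and weight is also assumed. In general the raw-AUC variance is SD(ln F)² + SD(ln weight)² − 2 × cov(ln F, ln weight). A negative covariance would widen the interval further. A positive covariance would shrink the excess and, above half of SD(ln weight)², would make the interval too narrow. The per-subject method does not depend on this assumption.

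The effect is modest, but it concerns the main objective and is worth correcting before analysis.

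**What to change.** Replace the sentence on geometric means in the Equation 1 legend with a per-subject definition:

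F_i = (AUC_patch,i / Dose_patch) / (AUC_IV,i / Dose_IV,i)

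Here AUC is AUC0-∞, Dose_IV,i is the mg dose actually administered to subject i, and Dose_patch is the total labelled content of the three patches (3 × 700 = 2,100 mg or 3 × 140 = 420 mg). Report the geometric mean of F_i for each patch. In section 10.4, state that the 95% interval is a t interval on ln F_i, back-transformed. The definition equals AUC_patch,i × CL_i / Dose_patch, with CL_i = Dose_IV,i / AUC_IV,i, so it uses a quantity that section 10.2 already estimates. It would also help to say that the two treatments in the legend are patch and IV, and that those in the section 10.4 model are the two patches.

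The cost is a wording change. Weight is recorded at screening and administration is documented (section 6.7); the administered mg dose only has to be carried into the analysis data. No procedure, blood sample or subject is added, and the patch-versus-patch model and the sample size stay as they are.
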